12.3.5.4. Efficacy Analyses

Anti-tumor activity for lymphoma subjects will be assessed based on the Response Criteria listed in Section 15.4. Anti-tumor activity for subjects with solid tumors will be assessed based on the Response Criteria listed in 15.5. Anti-tumor activity for subjects with MM will be assessed based on the Response Criteria listed in 15.6. Anti-tumor activity for subjects with prostate cancer will be assessed based on the Response Criteria listed in 15.7. The response data will be summarized by study part, and cohort within Part 2. Full details will be specified in the RAP.

If the data warrant, PFS and DoR will be calculated and listed for each subject in Part 1 and Part 2. PFS is defined as time from the date of first dose to the date of disease progression according to clinical or radiological assessment or death due to any causes, whichever occurs earliest. DoR is defined as the interval of time from first documented evidence of CR or PR until disease progression or death due to any cause. If the subject does not have a documented date of event, PFS will be censored at the date of the last adequate assessment. Further details on rules of censoring will be provided in the RAP. PFS will be summarized using the Kaplan-Meier method if the data warrant.

12.3.6. PK/PD Relationship

Observed or predicted concentrations or exposure measures (C_{max}, C_τ, AUC, or averaged observed concentration [C_{av}]) will be combined with safety, efficacy, exploratory markers and/or PD measures of interest to examine potential exposure response relationships.

The relationships will first be explored graphically. Where evidence of a signal is seen, linear and non-linear models may be fitted to the data to estimate PK/PD parameters of interest; slope, baseline (E₀), EC₅₀, and maximum effect (Emax).

12.3.7. Pharmacodynamic Biomarkers and Exploratory Response Prediction Biomarkers

As data warrant, analyses may be performed to explore the relationship between biomarkers (i.e., somatic mutations), subject baseline characteristics, and other clinical outcomes. All endpoints of interest will be descriptively and/or graphically summarized as appropriate to the data.

As data warrant, analyses may be performed to determine relationships between circulating and tumor biomarkers, expression and clinical response, activity, or resistance to GSK2816126.

The results of exploratory biomarker research investigations will be reported separately from the main clinical study report. Full details will be provided in a RAP.

13. STUDY CONDUCT CONSIDERATIONS

13.1. Posting of Information on Clinicaltrials.gov

Study information from this protocol will be posted on clinicaltrials.gov before enrollment of subjects begins.

13.2. Regulatory and Ethical Considerations, Including the Informed Consent Process

Prior to initiation of a study site, GSK will obtain approval from the appropriate regulatory agency to conduct the study in accordance with International Council on Harmonization/Good Clinical Practice (ICH/GCP) and applicable country-specific regulatory requirements.

The study will be conducted in accordance with all applicable regulatory requirements.

The study will be conducted in accordance with ICH GCP, all applicable subject privacy requirements, and the ethical principles that are outlined in the Declaration of Helsinki 2008, including, but not limited to:

- IRB/EC review and approval of study protocol and any subsequent amendments
- Subject informed consent
- Investigator reporting requirements

GSK will provide full details of the above procedures, either verbally, in writing, or both.

Written informed consent must be obtained from each subject prior to participation in the study.

In approving the clinical protocol the IEC/IRB and, where required, the applicable regulatory agency are also approving the optional assessments, e.g. genetic research described in [Appendix 5](#), unless otherwise indicated. Where permitted by regulatory authorities, approval of the optional assessments can occur after approval is obtained for the rest of the study. If so, then the written approval will clearly indicate approval of the optional assessments is being deferred and the study, except for the optional assessments, can be initiated. When the optional assessments are not approved, then the approval for the rest of the study will clearly indicate this and therefore, the optional assessments will not be conducted.

13.3. Urgent Safety Measures

If an event occurs that is related to the conduct of the study or the development of the IP, and this new event is likely to affect the study of subjects, the Sponsor, and the

investigator will take appropriate urgent safety measures to protect subjects against any immediate hazard.

The Sponsor will work with the investigator to ensure the IRB/EC is notified.

13.4. Quality Control (Study Monitoring)

In accordance with applicable regulations, GCP and GSK procedures, the site will be contacted prior to the start of the study to review with the site staff the protocol, study requirements, and their responsibilities to satisfy regulatory, ethical, and GSK requirements. When reviewing data collection procedures, the discussion will include identification, agreement and documentation of data items for which the eCRF will serve as the source document.

The investigator and the head of the medical institution (where applicable) agrees to allow the monitor direct access to all relevant documents and to allocate their time and the time to their staff to monitor to discuss findings and any issues.

Monitoring visits will be conducted in a manner to ensure that the:

- Data are authentic, accurate, and complete.
- Safety and rights of subjects are being protected.
- Study is conducted in accordance with the currently approved protocol and any other study agreements, ICH GCP, and all applicable regulatory requirements.

13.5. Quality Assurance

To ensure compliance with ICH/GCP and all applicable regulatory requirements, GSK may conduct quality assurance audits of the site. Regulatory agencies may conduct a regulatory inspection at any time during or after completion of the study. In the event of an audit or inspection, the investigator (and institution) must agree to grant the auditor(s) and inspector(s) direct access to all relevant documents and to allocate their time and the time of their staff to discuss any findings/relevant issues.

13.6. Study and Site Closure

The end of the study will be defined as the date of the last visit of the last subject enrolled.

Upon completion or termination of the study, the monitor will conduct site closure activities with the investigator or site staff (as appropriate), in accordance with applicable regulations, ICH/ GCP, and GSK Standard Operating Procedures.

GSK reserves the right to temporarily suspend or terminate the study at any time for reasons including (but not limited to) safety issues, ethical issues, or severe noncompliance. If GSK determines that such action is required, GSK will discuss the reasons for taking such action with the investigator or head of the medical institution (where applicable). When feasible, GSK will provide advance notice to the investigator or head of the medical institution of the impending action.

If a study is suspended or terminated for **safety reasons**, GSK will promptly inform all investigators, heads of the medical institutions (where applicable), and/or institutions conducting the study. GSK will also promptly inform the relevant regulatory authorities of the suspension/termination along with the reasons for such action. Where required by applicable regulations, the investigator or head of the medical institution must inform the IRB/EC promptly and provide the reason(s) for the suspension/termination.

GSK may also close study sites which fail to recruit subjects within a predefined timeframe, as defined within the Study Procedures Manual (SPM).

13.7. Records Retention

Following closure of the study, the investigator or head of the medical institution (where applicable) must maintain all site study records (except for those required by local regulations to be maintained elsewhere) in a safe and secure location. The records must be easily accessible when needed (e.g., for a GSK audit or regulatory inspection) and must be available for review in conjunction with assessment of the facility, supporting systems, and relevant site staff.

Where permitted by local laws/regulations or institutional policy, some or all of the records may be maintained in a format other than hard copy (e.g., microfiche, scanned, electronic); however, caution must be exercised before such action is taken. The investigator must ensure that all reproductions are legible and are a true and accurate copy of the original. In addition, they must meet accessibility and retrieval standards, including regeneration of a hard copy, if required. The investigator must also ensure that an acceptable back-up of the reproductions exists and that there is an acceptable quality control procedure in place for creating the reproductions.

GSK will inform the investigator of the time period for retaining the site records in order to comply with all applicable regulatory requirements. The minimum retention time will meet the strictest standard applicable to a particular site, as dictated by local laws/regulations, GSK standard operating procedures, and/or institutional requirements.

The investigator must notify GSK of any changes in the archival arrangements, including, but not limited to archival of records at an off-site facility or transfer of ownership of the records in the event that the investigator is no longer associated with the site.

13.8. Provision of Study Results to Investigators, Posting of Information on Publicly Available Clinical Trials Registers and Publication

Where required by applicable regulatory requirements, an investigator signatory will be identified for the approval of the clinical study report. The investigator will be provided reasonable access to statistical tables, figures, and relevant reports and will have the opportunity to review the complete study results at a GSK site or other mutually-agreeable location.

GSK will also provide the investigator with the full summary of the study results. The investigator is encouraged to share the summary results with the study subjects, as appropriate.

The results summary will be posted to the GSK Clinical Study Register no later than 8 months after the final primary completion date, the date that the final subject was examined or received an intervention for the purposes of final collection of data for the primary outcome. In addition, a manuscript will be submitted to a peer reviewed journal for publication no later than 18 months after the last subject's last visit (LSV). When manuscript publication in a peer-reviewed journal is not feasible, a statement will be added to the register to explain the reason for not publishing.

15. APPENDICES

15.1. Appendix 1: COCKCROFT-GAULT FORMULA

$$\text{ClCr (mL/min)} = \frac{Q \times (140 - \text{age[yr]}) \times \text{ideal body weight [kg]}^*}{72 \times \text{serum creatinine [mg/dL]}}$$

Q = 0.85 for females

Q = 1.0 for males

OR

$$\text{ClCr (mL/min)} = \frac{K \times (140 - \text{age[yr]}) \times \text{ideal body weight [kg]}^*}{\text{Serum creatinine [umol/L]}}$$

K = 1.0 for females

K = 1.23 for males

*Calculation of Ideal Body Weight Using the Devine Formula [Devine, 1974]

Ideal body weight:

Males = $50.0 \text{ kg} + (2.3 \text{ kg} \times \text{each inch over 5 feet})$ or $50.0 \text{ kg} + (0.906 \text{ kg} \times \text{each cm over 152.4 cm})$

Females = $45.5 \text{ kg} + (2.3 \text{ kg} \times \text{each inch over 5 feet})$ or $45.5 \text{ kg} + (0.906 \text{ kg} \times \text{each cm over 152.4 cm})$

Example: Male, actual body weight = 90.0 kg, height = 68 inches
Ideal body weight = $50.0 + (2.3) (68-60) = 68.4 \text{ kg}$.

This subject's actual body weight is >30% over ideal body weight. Therefore, in this case, the subject's ideal body weight of 68.4 kg should be used in calculating estimated CrCl.

Reference

Devine, BJ. Case Number 25 Gentamicin Therapy: Clinical Pharmacology Case Studies. Drug Intelligence and Clinical Pharmacy. 1974; 8:650-655.

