4. For all subjects: Availability of archival tissue, or willingness to undergo fresh biopsy if archival tissue is not available as described in Section 7.6.1.1, Section 7.6.1.2 and Section 7.6.5.
5. Must have a pre-existing central venous access such as a port, Hickmann catheter, or a peripherally inserted central catheter (PICC line) or be willing and able to have one inserted.
6. ECOG Performance Status of 0 or 1 (see [Appendix 2](#)).
7. Men with a female partner of childbearing potential must have either had a prior bilateral vasectomy with resultant azoospermia, bilateral orchiectomy, or must agree to use one of the contraception methods listed in Section 10.1 from the time of the first dose of study medication until at least 2 weeks (14 days) after the last dose of study treatment due to long elimination phase.
8. A female subject is eligible to participate if she is of:
 - Non-childbearing potential as defined in Section 10.1.1
 - Child bearing potential as defined in Section 10.1.1 and agree to use effective contraception, as defined in Section 10.1, for an appropriate period of time (as determined by the product label) prior to the start of dosing to sufficiently minimize the risk of pregnancy and for at least 2 weeks (14 days) following the last dose of study treatment. Women of childbearing potential must have a negative serum pregnancy test within 7 days of first dose of study treatment followed by negative urine or serum pregnancy test once every 4 weeks (prior to next dose cycle) thereafter.
9. Adequate organ system function as defined below:

System	LABORATORY VALUES
Hematologic	
ANC	≥1.2 x 10 ⁹ /L
Hemoglobin	≥9 g/dL
Platelets	≥75x 10 ⁹ /L
PT/INR and PTT	≤1.5 x ULN
Hepatic	
Albumin	≥2.5 g/dL
Total bilirubin	≤1.5 times ULN
AST and ALT	≤2.5 times ULN without liver metastases ≤5 times ULN if documented liver metastases
Renal	
Calculate Creatinine Clearance ^{a, b}	≥50 mL/min
Reproductive/Endocrine for CRPC only	
Testosterone	<50 ng/dL (only for subjects with CRPC)
Cardiac	
Left Ventricular Ejection Fraction (LVEF)	≥LLN (minimum of 50% LVEF) by ECHO or MUGA ^c

Abbreviation(s): ANC, absolute neutrophil count; ALT, alanine aminotransferase; AST, aspartate aminotransferase; ECHO, echocardiogram; INR, international normalization ratio, MUGA, multigated (radionuclide) angiogram; PT, prothrombin time, PTT, partial thromboplastin time, ULN, upper limit of normal, LLN, lower limit of normal.

- a. Calculated by Cockcroft-Gault formula

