- b. For MM subjects, adequate renal function is defined as calculated creatinine clearance ≥ 30 mL/min.
- c. ECHO is the preferred method and should always be used if available

NOTE: Laboratory results obtained during Screening should be used to determine eligibility criteria. In situations where laboratory results are outside the permitted range, the investigator may opt to retest the subject and the subsequent within range screening result may be used to confirm eligibility.

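### Appendix 1's two Cockcroft-Gault versions disagree for women by about 4%, and its weight rule is stated inconsistently, so the renal entry limit can give two answers for one patient

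*Protocol*

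**What the plan says.** Inclusion criterion 9 (Protocol Section 5.2.1, repeated in the Synopsis and carried into Part 2 by Section 5.2.2) sets a minimum creatinine clearance of 50 mL/min. Footnote a gives the method: "Calculated by Cockcroft-Gault formula". Footnote b lowers the limit to 30 mL/min for myeloma: "For MM subjects, adequate renal function is defined as calculated creatinine clearance". Section 5.2.1 also says that no deviation from the inclusion criteria is permitted.

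Appendix 1 (Section 15.1) supplies the formula in two forms, joined by OR:

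- Creatinine in mg/dL, divisor 72 x creatinine: "Q = 0.85 for females" and "Q = 1.0 for males".
- Creatinine in umol/L, divisor creatinine alone: "K = 1.0 for females" and "K = 1.23 for males".

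Both forms carry ideal body weight as the weight term, with an asterisk leading to "Calculation of Ideal Body Weight Using the Devine Formula". No condition is attached. The worked example is a man of 90.0 kg and 68 inches. It arrives at 68.4 kg and explains why ideal weight is used: "actual body weight is >30% over ideal body weight. Therefore, in this case".

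**The concern.** A fixed entry limit needs a calculation that returns one value per patient. Appendix 1 falls short of that in two ways.

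First, two versions offered as alternatives should differ only in units. The female-to-male ratio is 0.85/1.0 = 0.85 in the first and 1.0/1.23 = 0.813 in the second, so they cannot agree for both sexes.

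Second, the example treats ideal weight as the consequence of being more than 30% over it. That condition would be idle if ideal weight always applied. Yet the formulas attach no condition, and no weight is named for anyone at or below 30% over ideal.

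At stake is whether the same borderline patient is accepted at one site and refused at another, under criteria that allow no deviation.

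**Working it through.** **Inputs.** Factors, divisor and Devine weights are from Appendix 1; the limits of 50 and 30 mL/min are from Section 5.2.1. One input is assumed: 1 mg/dL creatinine = 88.4 umol/L, a unit conversion not printed in the protocol. The patients below are illustrative.

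**The plan's own example.** Ideal weight = 50.0 + 2.3 x (68 - 60) = 68.4 kg, as printed. 90/68.4 = 1.316, so 31.6% over ideal, as claimed. The example's arithmetic is right.

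**Unit versions.** For the two to give the same result, K must equal Q x 88.4/72.

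- Men: 1.0 x 88.4/72 = 1.228; printed 1.23. The ratio is 1.002, which is rounding only.
- Women: 0.85 x 88.4/72 = 1.0436; printed 1.0. The ratio is 1/1.0436 = 0.958, so the umol/L result is 4.2% lower.

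With a conversion factor between 88.0 and 88.42 the female shortfall is 3.7% to 4.2%, so the conclusion does not depend on the exact value.

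**Band in which the decision flips, women only.**

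- Limit 50: 50 x 1.0436 = 52.2. An mg/dL result from 50.0 to about 52.2 becomes a umol/L result below 50.
- Limit 30 (myeloma): 30 x 1.0436 = 31.3. The band is 30.0 to about 31.3.

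Example: woman aged 70, 64 inches, creatinine 0.90 mg/dL = 79.56 umol/L. Ideal weight = 45.5 + 2.3 x 4 = 54.7 kg.

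- mg/dL: 0.85 x 70 x 54.7/(72 x 0.90) = 50.2, eligible.
- umol/L: 1.0 x 70 x 54.7/79.56 = 48.1, not eligible.
- umol/L with K = 1.04: 48.13 x 1.04 = 50.05, eligible, in agreement with the mg/dL version.

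**Weight term.** Men aged 70, mg/dL version, ideal weight compared with actual weight:

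| Patient | Creatinine | Ideal weight | Clearance, ideal | Clearance, actual |
|---|---|---|---|---|
| 175 cm, 55 kg | 1.3 mg/dL | 50 + 0.906 x 22.6 = 70.5 kg | 70 x 70.5/(72 x 1.3) = 52.7 | 70 x 55/(72 x 1.3) = 41.1 |
| 68 in, 80 kg (17% over) | 1.4 mg/dL | 68.4 kg | 70 x 68.4/(72 x 1.4) = 47.5 | 70 x 80/(72 x 1.4) = 55.6 |

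The first man is eligible on ideal weight and not on actual weight; the second is the reverse. Clearance is proportional to weight, so for someone just under 30% over ideal the actual-weight figure is almost 30% higher.

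**The case against.** The best defence on weight is that a literal reader meets no conflict: both formulas say ideal weight, and the example also ends by using ideal weight. This stands in part. A reader might infer that the protocol means actual weight for everyone not more than 30% over ideal. The documents do not say so. The example gives a reason for using ideal weight in one patient and is silent on what applies to others, and actual weight is not the only alternative. A reader might also infer that the fault simply lets in thin patients whose clearance is too low. That presumes actual weight is correct, and it overlooks that an actual-weight rule would also admit heavier patients whom the printed formula refuses.

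On the female constant, the defence is about size. The gap is about 4%, it affects women only, and the umol/L version errs towards exclusion. The OR leaves sites free to use either version, and Section 5.2.1 lets an out-of-range screening result be retested. All of this limits the harm but does not make the two versions equal. Freedom to choose between them is itself a reason why they should agree.

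One might also derive the female K as 0.85 x 1.23 = 1.0455 and print 1.05. That carries forward the rounding already in 1.23; the direct conversion gives 1.0436, so 1.04 is the closer two-decimal value.

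Finally, creatinine clearance serves only as an entry check. The dose-adjustment rules in Sections 3.8.3 and 3.8.4 do not use it. That is correct and bounds the point.

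**Conclusion.** The point holds in two limited parts.

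- The female constant in the umol/L version does not match the mg/dL version. The shortfall is about 4.2%, and the entry decision reverses for women between 50.0 and about 52.2 mL/min, or 30.0 and about 31.3 in myeloma. This rests on the 88.4 conversion. The unequal sex ratios (0.85 against 0.813) show the mismatch without it.
- The weight wording is inconsistent between the formula line and the worked example. It can matter more than the constant and acts in both directions, but the documents do not settle which weight is intended. It is a contradiction to reconcile, not a demonstrated error in either direction.

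Both are confined to the renal entry criterion. No endpoint or stopping boundary depends on it.

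**What to change.** - In Appendix 1, set the female K in the umol/L version to 1.04, taking the mg/dL version as the reference. The remaining difference is 1.04/1.0436 = 0.997, about 0.3%. The cost is one constant, and a few borderline women become eligible at sites using umol/L.
- State the weight rule once and make the formula line and the example agree with it, including which weight applies to patients not more than 30% over ideal. The choice belongs to the sponsor. If ideal weight always applies, remove the conditional reasoning from the example. If it applies only above a threshold, put the condition in the formula line and name the other weight. The edit is one or two lines. The first option leaves the printed formulas unchanged. The second would change eligibility, and the sponsor should then check who is newly admitted as well as who is newly excluded.

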15.2. Appendix 2: ECOG Performance Status¹

CCI - This section contained Clinical Outcome Assessment data collection questionnaires or indices, which are protected by third party copyright laws and therefore have been excluded.

15.3. Appendix 3: Liver Chemistry Monitoring, Interruption Stopping and Follow-up Criteria

15.3.1. Liver Safety Stopping Criteria and Required Action and Follow up Assessments

Phase I/II liver chemistry stopping and increased monitoring criteria have been designed to assure subject safety and evaluate liver event etiology (in alignment with the FDA premarketing clinical liver safety guidance).

<http://www.fda.gov/downloads/Drugs/GuidanceComplianceRegulatoryInformation/Guidances/UCM174090.pdf>.

Phase I/II liver chemistry stopping criteria and required follow up assessments

Liver Chemistry Stopping Criteria – Liver Stopping Event Subject with entry criteria $ALT \leq 2.5 \times ULN$	
ALT-absolute	$ALT \geq 5 \times ULN$
ALT Increase	$ALT \geq 3 \times ULN$ persists for ≥ 4 weeks
Bilirubin^{1, 2}	$ALT \geq 3 \times ULN$ and bilirubin $\geq 2 \times ULN$ ($>35\%$ direct bilirubin)
INR²	$ALT \geq 3 \times ULN$ and $INR > 1.5$, if INR measured
Cannot Monitor	$ALT \geq 3 \times ULN$ and cannot be monitored weekly for 4 weeks
Symptomatic³	$ALT \geq 3 \times ULN$ associated with symptoms (new or worsening) believed to be related to liver injury or hypersensitivity
Liver Chemistry Stopping Criteria – Liver Stopping Event Including subjects with documented liver metastases/tumor infiltration at baseline AND entry criteria $ALT > 2.5 \times ULN$ but $\leq 5 \times ULN$	
ALT-absolute	Both $ALT \geq 5 \times ULN$ and $\geq 2 \times$ baseline value
ALT Increase	Both $ALT \geq 3 \times ULN$ and $\geq 1.5 \times$ baseline value that persists for ≥ 4 weeks
Bilirubin^{1, 2}	$ALT \geq 3 \times ULN$ and bilirubin $\geq 2 \times ULN$ ($>35\%$ direct bilirubin)
INR²	$ALT \geq 3 \times ULN$ and $INR > 1.5$, if INR measured
Cannot Monitor	Both $ALT \geq 3 \times ULN$ and $\geq 1.5 \times$ baseline value that cannot be monitored for 4 weeks
Symptomatic³	Both $ALT \geq 3 \times ULN$ and $\geq 1.5 \times$ baseline value associated with symptoms (new or worsening) believed to be related to liver injury or hypersensitivity
Required Actions and Follow up Assessments following ANY Liver Stopping Event	

Actions	Follow Up Assessments

 • Immediately discontinue study treatment • Report the event to GSK within 24 hours • Complete the liver event eCRF and complete an SAE data collection tool if the event also meets the criteria for an SAE² • Perform liver event follow up assessments • Monitor the subject until liver chemistries resolve, stabilize, or return to within baseline (see MONITORING below) • Do not restart/rechallenge subject with study treatment unless allowed per protocol and GSK Medical Governance approval is granted (refer to Appendix 3) • If restart/rechallenge is not granted, permanently discontinue study treatment and may continue subject in the study for any protocol specified follow up assessments 	
 • Viral hepatitis serology⁴ • Blood sample for pharmacokinetic (PK) analysis, obtained approximately 48 h after last dose⁵ • Serum creatine phosphokinase (CPK) and lactate dehydrogenase (LDH). • Fractionate bilirubin, if total bilirubin\geq2xULN • Obtain complete blood count with differential to assess eosinophilia • Record the appearance or worsening of clinical symptoms of liver injury, or hypersensitivity, on the AE report form • Record use of concomitant medications on the concomitant medications report form including acetaminophen, herbal remedies, other over the counter medications • Record alcohol use on the liver event alcohol intake case report form

MONITORING:

For bilirubin or INR criteria:

- Repeat liver chemistries (include ALT, AST, alkaline phosphatase, bilirubin) and perform liver event follow up assessments within **24 hrs**
- Monitor subjects twice weekly until liver chemistries resolve, stabilize or return to within baseline
- A specialist or hepatology consultation is recommended

For All other criteria:

- Repeat liver chemistries (include ALT, AST, alkaline phosphatase, bilirubin) and perform liver event follow up assessments within **72 hrs**
- Monitor subjects weekly until liver chemistries resolve, stabilize or return to within baseline

For bilirubin or INR criteria:

- Anti-nuclear antibody, anti-smooth muscle antibody, Type 1 anti-liver kidney microsomal antibodies, and quantitative total immunoglobulin G (IgG or gamma globulins).
- Serum acetaminophen adduct high pressure liquid chromatography (HPLC) assay (quantifies potential acetaminophen contribution to liver injury in subjects with definite or likely acetaminophen use in the preceding week [[James, 2009](#)]).
- Liver imaging (ultrasound, magnetic resonance, or computerised tomography) and /or liver biopsy to evaluate liver disease: complete Liver Imaging and/or Liver Biopsy eCRF forms.

1. Serum bilirubin fractionation should be performed if testing is available. If serum bilirubin fractionation is not immediately available, discontinue study treatment for that subject if ALT \geq 3xULN **and** bilirubin \geq 2xULN. Additionally, if serum bilirubin fractionation testing is unavailable, **record presence of detectable urinary bilirubin on dipstick**, indicating direct bilirubin elevations and suggesting liver injury.
2. All events of ALT \geq 3xULN **and** bilirubin \geq 2xULN ($>35\%$ direct bilirubin) or ALT \geq 3xULN **and** INR >1.5 , if INR measured which may indicate severe liver injury (possible 'Hy's Law'), **must be reported as an SAE (excluding studies of hepatic impairment or cirrhosis)**; INR measurement is not required and the threshold value stated

- will not apply to subjects receiving anticoagulants
3. New or worsening symptoms believed to be related to liver injury (such as fatigue, nausea, vomiting, right upper quadrant pain or tenderness, or jaundice) or believed to be related to hypersensitivity (such as fever, rash or eosinophilia)
 4. Includes: Hepatitis A IgM antibody; Hepatitis B surface antigen and Hepatitis B Core Antibody (IgM); Hepatitis C RNA; Cytomegalovirus IgM antibody; Epstein-Barr viral capsid antigen IgM antibody (or if unavailable, obtain heterophile antibody or monospot testing); Hepatitis E IgM antibody
 5. Record the date/time of the PK blood sample draw and the date/time of the last dose of study treatment prior to blood sample draw on the eCRF. If the date or time of the last dose is unclear, provide the subject's best approximation. If the date/time of the last dose cannot be approximated OR a PK sample cannot be collected in the time period indicated above, do not obtain a PK sample. Instructions for sample handling and shipping are in the SRM.

Phase I/II Oncology liver chemistry increased monitoring criteria with continued therapy

Liver Chemistry Increased Monitoring Criteria – Liver Monitoring Event	
Criteria	Actions

Subject with entry criteria ALT≤2.5x ULN ALT ≥3xULN but <5xULN and bilirubin <2xULN, without symptoms believed to be related to liver injury or hypersensitivity and who can be monitored weekly for 4 weeks
 
Subject with documented liver metastases/tumor infiltration at baseline AND entry criteria ALT>2.5 x ULN but ≤5 x ULN ALT ≥3x ULN and 1.5x baseline value but ALT <5x ULN and 2x baseline value and bilirubin <2xULN, without symptoms believed to be related to liver injury, or hypersensitivity and who can be monitored weekly for 4 weeks
	
 • Notify the GSK medical monitor within 24 hours of learning of the abnormality to discuss subject safety. • Subject can continue study treatment • Subject must return weekly for repeat liver chemistries (ALT, AST, alkaline phosphatase, bilirubin) until they resolve, stabilise or return to within baseline¹ • If at any time subject meets the liver chemistry stopping criteria, proceed as described above 
For subjects with entry criteria ALT≤2.5 x ULN
 
 • If, after 4 weeks of monitoring, ALT <3xULN and bilirubin <2xULN, monitor subjects twice monthly until liver chemistries normalize or return to within baseline. 
For subjects with documented liver metastases/tumor infiltration at baseline AND entry criteria ALT>2.5 x ULN but ≤5 x ULN
 
 • If, after 4 weeks of monitoring, ALT <3xULN and <1.5x baseline value, and bilirubin <2xULN, monitor subjects twice monthly until liver chemistries normalize or return to within baseline

1. For the purpose of these guidelines "baseline" refers to laboratory assessments performed closest and prior to first dose of study treatment

References

James LP, , Letzig L, Simpson PM, Capparelli E, Roberts DW, Hinson JA, Davern TJ, Lee WM. Pharmacokinetics of Acetaminophen-Adduct in Adults with Acetaminophen Overdose and Acute Liver Failure. *Drug Metab Dispos* 2009; 37:1779-1784.

